4.2 Scientific rationale for study design

Clinical studies typically exclude pregnant women and withdraw study participants once they become pregnant. This has created a lack of data regarding drug exposure that leaves both pregnant women and treating physicians without objective scientific evidence regarding dosing of CZP during pregnancy. Additionally, depending on the severity and condition, active disease can impact the outcome for the mother and infant and may necessitate therapy, even during pregnancy. For women who continue CZP therapy during pregnancy, there is no robust evidence available regarding the impact of pregnancy on PK during treatment with CZP. In order to ensure that women who require CZP treatment during pregnancy are able to achieve therapeutic steady state levels of CZP, it is valuable to conduct studies evaluating whether the physiologic changes underlying pregnancy impact exposure to CZP during pregnancy. This study (UP0085) will generate further data regarding steady state dosing of CZP during pregnancy, which can help to provide guidance on PK variability and the impact of pregnancy on CZP plasma levels.

The objective of this longitudinal, prospective, open label PK study is to assess any changes in CZP plasma concentrations that may result from physiological changes that occur during pregnancy. Women who take CZP for approved indications and maintenance dosing regimens (200mg every 2 weeks [Q2W] or 2 x 200mg Q4W or 400mg Q2W) and who continue with CZP treatment after they have become pregnant will be eligible to be considered for enrollment into this study, which will generate important information on CZP exposure during pregnancy. To measure CZP plasma concentration at steady state during pregnancy and after delivery, blood samples will be collected predose Q4W, postdose Q8W during the pregnancy, and 1 predose sample 12 weeks (\pm 1 week) postpartum (with potential postdose sample 1 week [\pm 1 day] after the postpartum sample). Each study participant will serve as her own control.

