- “n” will be an integer.
- Mean, SD, and median will use 1 additional decimal place compared to the original raw value from the Case Report Form (CRF).
- Coefficient of variance (CV [%]) will be presented with 1 decimal place.
- Minimum and maximum will have the same number of decimal places as the original raw value.

If the number of decimal places reported in the raw data is varied then either the maximum raw number of reported decimal places or 3 will be used, whichever is the lowest, as a guide for the descriptive statistics.

Unless stated otherwise, statistical tests will be performed 2-sided and p-values will be rounded to 4 decimal places. P-values less than 0.0001 will be presented as “<0.0001” and p-values greater than 0.9999 will be presented as “>0.9999.” Statistical comparison will be performed at the 0.05 level of significance.

The SAS® outputs supportive of any statistical model (i.e., all excluding the descriptive analyses) will be provided as a separate PDF document in addition to TFLs. These outputs will be included in the ‘Documentation of Statistical Methods’ section of the clinical study report.

The abbreviation for certolizumab pegol is CZP and will be used in tables and listings headers. Unless otherwise specified, in the TFLs study participants on Certolizumab pegol will be displayed in columns by dosing regimen and all study participants as:

- “Not Dosed”
- “CZP 200mg Q2W”
- “CZP 400mg Q2W”
- “CZP 400mg Q4W”
- “All Dosed Participants”

An additional “Other” category will be added to the tables in case there are dosing regimens outside those listed. The “Not Dosed” category includes participants who enrolled but did not record a CZP dose relative to any PK samples prior to discontinuation. The “All Dosed Participants” category includes participants in CZP 200mg Q2W, CZP 400mg Q2W and CZP 400mg Q4W combined.

Study Participants will be grouped according to the commercial CZP dosing regimen that was in effect at enrollment (actual dose). Any participant with a dose reduction or increase will be summarized in the initial dosing regimen group.

All repeated and unscheduled measurements will be presented in the data listings, where applicable. The following general rules will apply to all repeated and unscheduled measurements:

- Unscheduled measurements will not be used in the descriptive statistics.
- For repeated measurements only the scheduled latest value can be used in the calculation of the descriptive statistics.

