3.1.1 Summary statistics specific to PK data

For CZP Plasma concentrations, geometric mean, geometric coefficient of variation (geometric CV (%)), 95% CI for the geometric mean (assuming log-normally distributed data) will only be calculated if at least $\frac{2}{3}$ of the values of interest are above the LLOQ (0.032 ug/mL). If this is not the case, only median, minimum and maximum will be presented.

The 95% CI for the geometric mean will be calculated by obtaining the lower and upper 95% CI for the arithmetic mean on the log-transformed data and back-transforming to obtain the respective values for the geometric CI.

The geometric CV (%) will be calculated using the following formula:

$$CV = \sqrt{e^{SD_{ln}^2} - 1}$$

where SD_{ln} represents the standard deviation of the log-transformed plasma concentration values.

The intraclass correlation coefficient (ICC) will be calculated using the following formula:

$$\rho = \frac{\sigma_r^2}{\sigma_r^2 + \sigma_\epsilon^2}$$

Where σ_r^2 represents the variance of the random effect and σ_ϵ^2 represents the variance of the residual in the linear mixed effects model as described in Section 9.1.2.

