9.1.2 Primary analysis of the primary outcome variable

The CZP plasma concentrations (primary variable) will be analyzed using a linear mixed effects model with fixed effects for disease phenotype, gestational week, trimester [trimester 1, 2, 3, or postpartum] and whether the sample was predose or postdose [binary indicator], and the random effect will be study participant. Within this model trimesters will be defined as follows: trimester 1 (≤ 12 weeks and 6 days' gestation), trimester 2 (13–28 weeks and 6 days' gestation), trimester 3 (≥ 29 weeks' gestation) and postpartum.

A compound symmetry covariance structure will be used, as this was decided to be the most appropriate structure given the context of this data. In case of overfitting, disease phenotype will be excluded from the model.

Adjusted mean differences with 95% CI of CZP plasma concentrations between samples taken each pregnancy trimester and postpartum will be estimated within this linear mixed effects model using contrasts. These adjusted mean differences and 95% CIs will be displayed graphically in a forest plot.

ICC may be provided to describe the consistency of CZP absorption from the same participant based on the linear mixed effects model as described in Section 3.1.1.

Data analyses may be conducted on log-transformed data, based on visual inspection of the data. This will be based on visual inspection of histograms, boxplots and quantile-quantile plots for each dosing regimen which will be included as part of the statistical appendices. If the data show a departure from normality, data analysis will be conducted on log transformed data (and back-transformed results displayed).

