9.1.4 Exploratory analysis of the primary outcome variable

The linear mixed effects model from the primary analysis will also be fitted to the predose and postdose CZP plasma concentrations separately. Adjusted means and 95% CI for each model will be included in the forest plot.

CZP plasma concentrations will additionally be analyzed adjusting for CRP, albumin and BMI. These analyses will be conducted using the same linear mixed effects model used for the primary analysis with CRP, albumin and BMI as a covariate in 3 separate models. Results from these models should be interpreted with caution, due to the small sample size and relatively large number of covariates. Summary tables showing the mean differences and 95% CIs of each trimester vs post-partum estimated from the model contrasts will be presented.

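### The primary model has no term for a pregnancy effect that differs between women, so the trimester-versus-postpartum intervals can be too narrow

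*SAP*

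**What the plan says.** The primary analysis (SAP 9.1.2) is a linear mixed model with fixed effects for disease phenotype, gestational week, trimester (1, 2, 3 or postpartum) and dose point. For the random part, "the random effect will be study participant", and "A compound symmetry covariance structure will be used". The reason given is that "this was decided to be the most appropriate structure" in the context of the data, with no further argument. The intraclass correlation formula in SAP 3.1.1 confirms that there are only two variance components: one term "represents the variance of the random effect and" the other is the residual variance.

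The reported result is "Adjusted mean differences with 95% CI of CZP plasma concentrations between samples taken each pregnancy trimester and postpartum", shown in a forest plot. Protocol 4.2 describes the comparison as within-woman: "Each study participant will serve as her own control".

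The exploratory models in SAP 9.1.4 keep the same structure, split by dose point or with "CRP, albumin and BMI as a covariate in 3 separate models". Neither document specifies a random slope, a participant-by-period term, a robust standard error, a small-sample degrees-of-freedom method or a sensitivity analysis for the covariance choice.

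Gestational week is continuous (SAP 4.1) and counted from the last menstrual period, or back-calculated from the birth record after IVF (SAP 3.2.2). Its value for postpartum samples is not stated.

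**The concern.** In a design where each woman is her own control, the uncertainty of the mean change includes how much that change differs from woman to woman. A participant intercept removes differences in level only. Each woman gives about nine pregnancy samples (six predose, three postdose) against one or two postpartum samples. The model treats the nine as separate pieces of evidence on a shift that she contributes once.

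Variation in the shift is plausible on the plan's own terms. Protocol 6.6 allows the regimen to be modified after entry with follow-up continuing. SAP 3.1 keeps such women in their initial regimen group, and regimen is not among the covariates in SAP 4.1. In addition, SAP 9.1.1 analyses concentrations as measured unless a log transformation is judged necessary. On that scale, even an identical percentage change gives unequal absolute changes when starting levels differ.

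At stake is the precision claimed for the primary estimates, which Protocol 2.2 intends as information for women and physicians.

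**Working it through.** **Inputs from the documents.** About 15 evaluable women (Protocol 9.8, SAP 2.4); about 6 predose and 3 postdose pregnancy samples each; one postpartum predose sample and an optional postdose sample; nominal coverage 95%.

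**Assumptions, not in the documents.** tau is the between-woman SD of the pregnancy effect and sigma the residual SD. With sigma = 0.3 on the log scale, tau of 0.15, 0.25 and 0.35 correspond to tau/sigma of 0.5, 0.83 and 1.17.

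**How tau could reach 0.25.** Suppose exposure is proportional to dose, and 2 of 15 women have a twofold different dose rate throughout pregnancy compared with postpartum. A twofold change is ln 2 = 0.693, so tau = 0.693 × √(2/15 × 13/15) = 0.24. This is an illustration, not an estimate.

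**Closed form (balanced data, no week term).** Per woman, let nP be the pregnancy samples, nT those in the trimester of interest and nPP the postpartum samples.

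- Variance the model reports: (1/nT + 1/nPP)(sigma² + c·tau²)/N, with c = [nP·nPP/(nP + nPP)]/(nP + nPP − 1)
- True variance: [(1/nT + 1/nPP)sigma² + tau²]/N

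At tau = sigma, in units of sigma²/N:

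- nP = 9, nT = 4, nPP = 2: c = (18/11)/10 = 0.164. Reported 0.75 × 1.164 = 0.873; true 0.75 + 1 = 1.75. SE ratio √(0.873/1.75) = 0.706; coverage 2Φ(1.96 × 0.706) − 1 = 83.4%.
- nP = 9, nT = 2, nPP = 1: c = (9/10)/9 = 0.1. Reported 1.5 × 1.1 = 1.65; true 1.5 + 1 = 2.5. SE ratio √(1.65/2.5) = 0.812; coverage 88.9%.

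At tau/sigma = 0.5 the same two layouts give 91.7% and 93.4%. N cancels from the ratio, so more women do not cure the problem.

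**Simulation (REML, 15 women, 1,500 trials per case, optional postpartum sample present in 70%).** At tau = 0 the nominal 95% is reproduced: 94.1-95.9% under all three treatments of week. LMP is the last menstrual period.

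| Gestational week | tau/sigma | T1 | T2 | T3 |
|---|---|---|---|---|
| Not in model | 0.5 | 93.2% | 91.9% | 91.8% |
| Not in model | 1 | 86.9% | 82.7% | 83.7% |
| Not in model | 1.5 | 79.8% | 74.1% | 75.9% |
| In model, postpartum constant | 1 | 91.3% | 83.9% | 91.1% |
| In model, postpartum constant | 1.5 | 87.7% | 72.7% | 86.7% |
| In model, weeks since LMP | 1 | 95.8% | 95.0% | 93.3% |
| In model, weeks since LMP | 1.5 | 96.3% | 95.4% | 91.4% |
| Weeks since LMP, effect grows with gestation | 1 | 95.6% | 94.3% | 90.9% |
| Weeks since LMP, effect grows with gestation | 1.5 | 93.6% | 91.3% | 84.1% |

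With weeks since LMP a postpartum sample sits at about week 51-53, so the contrast becomes an extrapolation. At tau/sigma = 1 the half-widths are 2.17/1.60/1.03 sigma (T1/T2/T3) against 0.58/0.49/0.53 without week, roughly 2 to 4 times as wide. This largely hides the missing variance.

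**Separate check at sigma = 0.3, tau = 0.35 (200 trials per case, about 2 points of Monte Carlo error).** T3 coverage is 80% without week; 86% with postpartum constant (T2 84%, and 80% in another run); about 93% with weeks since LMP and a constant shift; and 74% with that coding if the effect grows. A different growth pattern gave 87-88% at tau 0.25-0.35, so the last figure depends on how growth is modelled.

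**The case against.** The mechanism is not in dispute; the size is. A reader might infer that the plan's intervals are certainly too narrow, or that their coverage is around 80%. The documents support neither. They give no value for the between-woman SD of the pregnancy effect. Coverage that low under a constant shift comes mostly from a model without gestational week, and SAP 9.1.2 includes week. With the literal coding, weeks since the last menstrual period, T1 and T2 stay near nominal under a constant shift and T3 loses only a few points. That objection stands. It does not remove the concern: T2 falls under the constant coding, and T3 falls under the literal coding if the effect grows through pregnancy.

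A reader might also infer an inflated type I error, since SAP 3.1 says "Statistical comparison will be performed at the 0.05 level of significance". That is a general presentation rule. SAP 2.4 states that no formal hypothesis testing is planned, and Protocol 4.1 calls the study exploratory.

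It is also tempting to argue that compound symmetry fails because samples close in time should correlate more than distant ones. That is a different matter, and a pregnancy-versus-postpartum effect would leave all pregnancy samples equally correlated with one another.

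Nor do the documents say outright that the effect varies. CRP, albumin and BMI enter as main effects; permitted regimen change is the firmest ground.

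Finally, the individual and spaghetti plots, the geometric mean intervals built on one average per woman per trimester (SAP 9.1.3) and the population PK analysis (Protocol 9.3.1) can reveal variation. They do not alter the primary intervals.

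**Conclusion.** The concern holds in a conditional form: the primary model cannot represent a pregnancy effect that differs between women, and if it does differ, the trimester-versus-postpartum intervals can be too narrow. For 15 women, sigma = 0.3 and tau = 0.25-0.35, coverage is:

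- about 77-87% if week is left out;
- about 84-95% with week included and postpartum held constant, T2 being worst;
- about 92-96% with weeks since LMP under a constant shift, falling to about 74-85% for T3 if the effect grows with gestation (87-88% under another growth pattern).

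At tau = 0.15 the loss is only a few points. The harm is overstated precision of the primary estimate in an exploratory study. This is a cheap improvement worth making, not a flaw that invalidates the analysis.

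**What to change.** In SAP 9.1.2:

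1. State the value of gestational week assigned to postpartum samples.
2. Add a woman-specific pregnancy-versus-postpartum random effect with a small-sample degrees-of-freedom method. Alternatively, report per-woman paired contrasts (trimester mean minus own postpartum value, same dose point) with a t interval.
3. Show the compound symmetry result alongside.

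In simulation without week, the added effect gave coverage of 94-98% at tau/sigma from 0.5 to 1.5 (300 trials per case). With weeks since LMP at tau/sigma = 1 it gave 94-96%. It does not fully restore T3 coverage if the effect grows through pregnancy. The paired interval covered 93.5-96% in all cases and is the more robust check.

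No new data or visits are needed. The cost is width. With no heterogeneity the intervals are about 4-10% wider. Without week at tau/sigma = 1, half-widths go from 0.58/0.49/0.53 to 0.80/0.73/0.77 sigma, which is 38%, 49% and 45% wider; overall, expect roughly 40-60% when heterogeneity is substantial (tau of about 0.35). With weeks since LMP at tau/sigma = 1 they go from 2.17/1.60/1.03 to 2.29/1.73/1.19 sigma, about 6-16% wider. Under heterogeneity, the extra width is mainly uncertainty that the current model leaves out.

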9.1.3 Primary summaries of the primary outcome variable

The individual plasma concentrations of CZP (ug/mL) will be summarized over the course of pregnancy by dosing regimen and by trimester or dosing time point (predose or postdose) using graphs and descriptive statistics (number of observations [n], geometric mean, lower and upper 95% confidence intervals [CI], geometric CV, arithmetic mean, SD, median, minimum, and maximum values).

The graphs to be produced by dosing regimen include:

1. Individual CZP plasma concentration plots using gestational week with predose and postdose values plotted side by side,

2. Spaghetti plots of CZP plasma concentrations using gestational week with predose and postdose values plotted side by side, and
3. Geometric Mean plots by dosing regimen and sample time relative to dose, i.e., separately for predose and postdose. The time points will be based on trimester as defined in Section 3.2.2, including the postpartum period. The plot will show both a linear and semi-logarithmic scale side by side. The average predose (or postdose) results within trimester per participant will be used to calculate the geometric mean and 95% CI for all participants combined.

For the calculation of descriptive statistics, a plasma concentration below the lower limit of quantification (LLOQ) will be substituted by LLOQ/2. The geometric and arithmetic means and associated SD, lower and upper limits of 95% CI, and CV will be calculated only if at least two thirds of the individual data at a specific sampling point are measured, are above or equal to LLOQ, and $n \geq 4$. If $n < 4$, a subset of summary statistics will be displayed as described in Section 3.1.

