9.3.1 Pharmacokinetic analyses

All PK analyses will be performed on the PK-PPS. The individual plasma concentrations of CZP will be summarized over the course of pregnancy by trimester and dosing time point (predose or postdose) using graphs and descriptive statistics (number of observations [n], geometric mean, lower and upper 95% confidence intervals [CI], geometric CV, arithmetic mean, SD, CV, median, minimum, and maximum values).

For the calculation of descriptive statistics, a plasma concentration below the lower limit of quantification (LLOQ) will be substituted by LLOQ/2. The geometric and arithmetic means and associated SD, lower and upper limits of 95% CI, and CV will be calculated only if at least two-thirds of the individual data at a specific sampling point are measured, are above or equal to LLOQ, and $N \geq 4$.

The CZP plasma concentrations (primary variable) will be analyzed using a linear mixed effect model (disease phenotype, time point, trimester [trimester 1, 2, 3, or postpartum] and whether the sample was predose or postdose [binary indicator] may be used as fixed effects, and the random effect will be study participant). Mean differences with 95% CI of CZP plasma concentrations between samples taken during pregnancy and baseline (predose measurement at 12 weeks (± 1 week) postpartum and potential postdose sample 1 week [± 1 day] after the predose postpartum sample) will be estimated within this mixed effect model using contrasts. A forest plot of mean trough CZP plasma concentrations with 95% CI of each sampling time point during pregnancy and postpartum will be displayed. Data analysis may be conducted on log-transformed data (and back-transformed results displayed). Then, the change from baseline in CZP plasma concentrations across trimesters will be adjusted for the clinical covariates of albumin, body mass index (BMI), CRP (or any other relevant covariates) and disease phenotype using a multivariate linear mixed-effects model. The resulting coefficient b-estimate represents the change in CZP plasma concentrations for a unit increase in that predictor.

Pharmacokinetic data from this study will also be analyzed using population PK methodologies, which will enable derivation of (posthoc) PK parameters throughout the study periods, as well as enable accounting for individual variations in dosing regimens and times.

Any additional analyses may be defined in the SAP.

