1 INTRODUCTION

This statistical analysis plan (SAP) provides the necessary information to perform the final statistical analysis for study UP0085. It also defines the summary tables, figures and listings (TFLs) to be generated for the final clinical study report.

The SAP is based on the final Protocol Amendment 2 (30 AUG 2022). All references to study protocol hereafter refer to this version of the protocol, and, unless otherwise specified, the study will be analyzed as described in this version of the protocol. If a future protocol amendment necessitates a substantial change to the statistical analysis of the study data, or if analysis definitions must be modified or updated, this SAP will be amended accordingly.

The content of this SAP is compatible with the International Council for Harmonization (ICH)/Food and Drug Administration (FDA) E9 Guidance documents (Phillips et al, 2003).

The study assesses any changes in certolizumab pegol (CZP) plasma concentrations over the course of pregnancy, relative to the postpartum period. CZP is approved in adults for the treatment of chronic inflammatory diseases. It is valuable to evaluate whether the physiologic changes underlying pregnancy impact the pharmacokinetic (PK) profile of CZP during pregnancy in order to ensure that women who require CZP treatment during pregnancy are able to achieve therapeutic steady state levels of CZP.

Revision(s) of this SAP will not be required for any subsequent amendments to the protocol which do not change the analyses described in this SAP.

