3.9 Changes from protocol-defined analyses

The following change from the protocol have been implemented in the SAP:

- The protocol stated the secondary outcome variable of 'adverse events from time of informed consent through Safety Follow-up', this will now be 'Treatment-emergent adverse events from time of informed consent through Safety Follow-up'.
- The protocol defines 'baseline' for plasma concentration data as the predose measurement 12 weeks (± 1 week) postpartum. In the SAP, tables and figures, the name for the reference point was changed to 'postpartum'.

- Clarification was added to the Enrolled Set definition to include participants who re-enrolled. The SS definition was updated to include all participants with ongoing CZP dosing at screening. PK-PPS definition was clarified to include participants for whom at least one predose or postdose sample is available which was not impacted by an important protocol deviation.

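### In three rows of the descriptive PK tables (trimester 2 predose and postdose, trimester 3 predose), the 95% CI of the geometric mean treats a woman's repeated samples as independent and is too narrow

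*SAP*

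**What the plan says.** The table content is set in SAP 9.1.3: individual concentrations, summarised with "descriptive statistics (number of observations [n], geometric mean, lower and upper 95% confidence intervals [CI], geometric CV" and further statistics. In this list n is the number of samples. SAP 3.1.1 obtains the interval for the geometric mean by back-transforming the "lower and upper 95% CI for the arithmetic mean on the log-transformed data". Neither section has a term for several samples from one woman.

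Within-woman averaging appears only under the third graph of SAP 9.1.3: "The average predose (or postdose) results within trimester per participant will be used to calculate the geometric mean and 95% CI". It is not extended to the tables.

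Means and CIs are shown "only if at least two thirds of the individual data at a specific sampling point are measured, are above or equal to LLOQ", and only with n of at least 4. For smaller n the text refers to SAP 3.1, where n is by default the number of participants. Protocol 9.3.1 gives the same threshold with a capital, undefined N.

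The layout differs between the documents. The SAP has "by dosing regimen and by trimester or dosing time point (predose or postdose"), the protocol "by trimester and dosing time point (predose or postdose").

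The primary model in SAP 9.1.2 has a participant random effect with compound symmetry.

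**The concern.** A one-sample CI is valid when the values in the row are independent. Predose samples taken from the same woman every 4 weeks are not expected to be. The SAP accepts this elsewhere, through the participant random effect, the ICC formula in SAP 3.1.1 and the averaging in the third graph. Only the tables leave it out.

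At stake is the apparent precision of the descriptive table for the primary endpoint. A reader comparing trimester 2 with postpartum would see a trimester CI that is too tight beside a postpartum CI that is about right. The same regimen, trimester and dosing time point could also carry one CI in the table and another in the plot.

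**Working it through.** **Step 1: samples per woman.** Inputs: predose every 4 weeks, postdose every 8 weeks and about 6 and 3 samples expected (Protocol 1.1, SAP 2.3); trimester limits (SAP 3.2.2).

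The plan's own figure can be reproduced. With the first sampled dose at week 14 and delivery at week 37, predose samples fall at weeks 14, 18, 22, 26, 30 and 34 (6). Postdose samples fall at weeks 15, 23 and 31 (3). That is 4 predose and 2 postdose in trimester 2, and 2 predose and 1 postdose in trimester 3.

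More generally:
- Trimester 2 runs from 13w0d to 28w6d, which is 16 weeks: 16/4 = 4 predose and 16/8 = 2 postdose.
- Trimester 3 runs from week 29 to delivery. With delivery assumed at weeks 38–40 it lasts 9–11 weeks: 9/4 to 11/4 gives 2–3 predose, and 9/8 to 11/8 gives 1–2 postdose. The count is 1 postdose in roughly 70–80% of schedules, depending on the enrolment and delivery weeks assumed.
- Trimester 1 has 0–2 predose and 0–1 postdose samples.
- Postpartum has one of each at most.

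These counts assume no missing samples. Protocol Table 1–1, footnote a, expects some to be missing, so they are upper cases.

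**Step 2: the two intervals.** Let there be N women, m samples each, log-scale total SD σ and intraclass correlation ρ.
- Sample-level half-width, as the SAP text reads: t(Nm−1) × SD of samples / √(Nm).
- Woman-level half-width: t(N−1) × SD of woman means / √N.
- True variance of the log mean: σ²[1 + (m−1)ρ]/(Nm). The sample-level interval omits the bracket.

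For m = 4 and ρ = 0.5 the bracket is 1 + 3 × 0.5 = 2.5. A large-sample check gives 1.96/√2.5 = 1.24, or about 78% coverage.

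**Step 3: coverage of the nominal 95% sample-level CI** (log-normal data, random intercept per woman, simulation). The documents give no ICC, so a range is assumed.

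| N = 10, full sampling | ICC 0.1 | 0.3 | 0.5 | 0.7 | 0.9 |
|---|---|---|---|---|---|
| m = 2 (T2 postdose, some T3 predose) | 94% | 91% | 89% | 86% | 83% |
| m = 3 (other T3 predose) | 93% | 88% | 83% | 78% | 74% |
| m = 4 (T2 predose) | 91–92% | 84% | 78% | 72% | 67% |

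- The woman-level CI covers about 95% in every setting.
- With 25% of samples missing at random (assumed), N = 10 and ICC 0.3–0.9: 93–86%, 90–78% and 87–72% for m = 2, 3 and 4.
- With 15 evaluable women split equally over three regimens (assumed), 15/3 = 5 per column. Under full sampling coverage is then 92–82% for m = 2 and 84–64% for m = 4.

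**Step 4: on the concentration scale.** Assume a geometric CV of 40%, so σ = √ln(1 + 0.4²) = 0.385, with ICC 0.7 and m = 4. The bracket is 1 + 3 × 0.7 = 3.1.
- N = 10, sample level: 2.023 × 0.385/√40 = 0.123, so the geometric mean ×/÷ 1.13.
- N = 10, woman level: 2.262 × 0.385 × √(3.1/40) = 0.243, so ×/÷ 1.28.
- N = 5: ×/÷ 1.20 becomes ×/÷ 1.52.

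**The case against.** The strongest defence is that little depends on these intervals. The study is exploratory and has no formal hypothesis test. The trimester-versus-postpartum comparison comes from the mixed model, and a woman-level CI is already planned in the third graph. SAP 3.1 takes n as participants by default, so a programmer might average within woman anyway. The protocol itself asks for individual concentrations and the number of observations. The ICC is unknown, and at 0.1 the loss is small.

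Most of this stands and limits the weight of the point. It does not remove it, because SAP 9.1.3 says observations and confines the averaging to one graph.

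Three stronger readings are tempting, and the documents do not support them:
- A reader might infer that the pregnancy-versus-postpartum estimates are too precise for the same reason. They are not affected by it: SAP 9.1.2 and 9.1.4 use a participant random effect.
- A reader might infer that one woman's four trimester 2 samples would satisfy the n ≥ 4 rule and earn a CI. The text does not settle this. SAP 9.1.3 defines n as observations, but SAP 3.1 points to participants and the protocol's capital N may do so too. What holds is that the rule is ambiguous.
- A reader might infer from the SAP's layout wording that predose and postdose samples are to be pooled. SAP 3.9, which opens "The following change from the protocol have been implemented in the SAP", lists no such change, and SAP 1 says that "unless otherwise specified, the study will be analyzed as described in this version of the protocol". A slip is the likelier explanation, though the two texts still need reconciling.

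**Conclusion.** The point holds for three rows, given a table split by predose and postdose as in the protocol: trimester 2 predose, trimester 2 postdose and trimester 3 predose. Trimester 3 postdose, with mostly one sample per woman, and trimester 1 are little affected. Postpartum is not affected.

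The direction is certain for any positive within-woman correlation. The size rests on an assumed ICC of 0.3–0.9, about 10 women and full sampling. It ranges from a few points of lost coverage with 2 samples per woman at low ICC to coverage of about two thirds with 4 samples at ICC 0.9. Missing samples reduce the loss and a low ICC makes it small. The consequence is confined to displayed descriptive CIs, so this is a minor point, worth correcting because the remedy is short.

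**What to change.** In SAP 9.1.3:

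1. For trimester rows, compute the geometric mean and its 95% CI from one log-scale average per woman within regimen, trimester and dosing time point. Use the same average in the third graph, whose averaging scale is not stated now. Do likewise for any CI of the arithmetic mean.
2. Show the number of women and the number of samples, and state that the n ≥ 4 rule for showing a CI counts women.
3. Label the CV, SD, median, minimum and maximum as sample-level, since the CI can no longer be derived from them and the sample count. Keep the two-thirds-above-LLOQ rule on samples.
4. List this in SAP 3.9 as a change from Protocol 9.3.1, and reconcile the SAP's layout wording with the protocol's split by trimester and dosing time point.

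The cost is SAP wording plus averaging that the third graph already needs. Displayed CIs become wider. If samples were truly independent, the unnecessary widening for 2–4 samples per woman would be about 7–9% with 10 women and 19–26% with 5. Columns with fewer than 4 women show no CI. Each woman gets equal weight, so with missing samples the geometric mean can differ slightly from the sample-level value.
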